**20.0 Statistical Analysis**

At least 66 evaluable patients will be randomized (1:1 allocation, 33 evaluable patients in each arm) into "anticoagulation" versus "anticoagulation +atorvastatin" arms. The primary endpoints are thrombin peak and thrombin generation. Based on the published data, we anticipate an 80% power to detect an effect size of 0.7 standard deviations in the reduction of thrombin peak or thrombin generation between the two arms with two-side alpha of 0.05 using a two-sample t test. An overall alpha of 0.1 for this pilot study was split into 0.05 for each endpoint (thrombin peak and thrombin generation) using Bonferroni method. Considering possible drop-outs, our target enrollment will be 80 patients, with 40 on each arm.

All data will be collected on study-approved data collection forms and entered into Research Electronic Data Capture (REDCap), which is a secure, web-based application designed to support data capture for research studies by building and managing online surveys and databases. The system was built with the help of the OSU Research Informatics Services.

Descriptive statistics (i.e. means, standard deviations, 95% confidence intervals for continuous variables, and frequencies for discrete data) and graphical analyses will be used for all clinical outcomes, demographics, VTE related events, laboratory results, and adverse events for each arm. The secondary endpoints will be compared between the two arms using chi-square test or Fisher's exact test, whichever is appropriate. The associations between treatment type and the change in biomarkers will be evaluated using two-sample t test. Log-transform will be used if necessary. Linear mixed models will be used to study the associations between the primary endpoints and treatment, and trend across time. The interaction term "arm x time" will be included in the model to study whether the two treatment arms have different "behavior" across time. Potential confounders will be included in the models. Thrombin peak concentration and

endogenous thrombin potential at 9 months will be compared between the patients on anticoagulation and those off anticoagulation.

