### 1.1 Primary Objective

1.1.1 To determine the reduction of thrombin peak concentration and/or endogenous thrombin potential measured by Thrombin Generation Assay (TGA) at 3 months in the “anticoagulation +atorvastatin” arm as compared to the “anticoagulation” arm.

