## 6.0 Study calendar

	Initial visit	3 month 	9 month 
Singed informed consent	x		
Medical/treatment history	x	x	x
Physical examination	x	x	x
Vital signs	x	x	x
CBC with diff	x	x	x
Chemistry, including liver function tests	x	x	x
Fasting lipid profiles	x	x	x
hs-CRP	x	x	x
D-dimer	x	x	x
Urine <math>\beta</math>-hCG	x		
Thrombin generation assay	x	x	x
IL-6, IL-8, TNF-<math>\alpha</math>	x	x	x
Lipidomic profiles	x	x	x
Doppler ultrasound of bilateral lower extremities		x	
Prescription of statins	x	x	

All scheduled visits are allowed a window of +/- 21 days

CBC includes: white blood cells with differential, hemoglobin, red blood cells, and platelets

Chemistry and liver function tests include: sodium, potassium, carbon dioxide, glucose, BUN, creatinine, calcium, total protein, albumin, bilirubin, alkaline phosphatase, AST and ALT

Required only in women of child-bearing potential

Lipidomic profiles includes free fatty acids, lipoprotein-associated phospholipase A2, pro-inflammatory eicosanoids

Prescription of statins only in the statin arm

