## **9.0 Correlative Studies**

### **9.1 Laboratory Studies at Enrollment**

9.1.1 The initial laboratory tests will be obtained at the time of enrollment on this study. Blood will be collected after overnight fasting for at least 9 hours. Laboratory tests will include:

- CBC (complete blood count)
- chemistry panel (Na, K, Cl, CO2, Cr, BUN, Ca, and glucose),
- liver function tests (AST, ALT, ALP, total and direct bilirubin)
- D-dimer
- high-sensitivity C-reactive protein (hs-CRP)
- fasting lipid profiles (LDL, HLD, TG, total cholesterol)
- β-hCG is required only in women of child-bearing potential

*Research labs:*

- thrombin generation assay
- IL-6, IL-8, tumor necrosis factor (TNF)-α
- lipidomic profiles including free fatty acids, lipoprotein-associated phospholipase A2, pro-inflammatory eicosanoids
- plasma levels and RNA expression of tissue factor (TF), tissue factor pathway inhibitor (TFPI), and other clotting factors

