### **9.2 Subsequent Follow-up and Correlative Laboratory Studies**

9.2.1 All enrolled patients will be seen on enrollment and at month 3 and 9.

9.2.2 The following laboratory studies will be obtained at each follow-up visit:

- CBC (complete blood count), platelet count
- chemistry panel (Na, K, Cl, CO2, Cr, BUN, Ca, and glucose),
- liver function tests (AST, ALT, ALP, total and direct bilirubin)
- d-dimer
- high-sensitivity C-reactive protein (hs-CRP)
- fasting lipid profiles (LDL, HLD, TG, total cholesterol)

*Research labs:*

- thrombin generation assay
- IL-6, IL-8, tumor necrosis factor (TNF)- $\alpha$
- lipidomic profiles including free fatty acids, lipoprotein-associated phospholipase A2, pro-inflammatory eicosanoids
- plasma levels and RNA expression of tissue factor (TF), tissue factor pathway inhibitor (TFPI), and other clotting factors

9.2.3 A follow up Doppler ultrasound will be obtained at month 3 as standard of care in all patients to evaluate residual vein thrombosis.

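### Section 20.0 names no primary 3-month analysis and no role for baseline thrombin generation; a baseline-adjusted ANCOVA would settle both at almost no cost.

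*Combined protocol and SAP*

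**What the plan says.** Section 1.1 sets the primary question: "To determine the reduction of thrombin peak concentration and/or endogenous thrombin potential measured by Thrombin Generation Assay (TGA) at 3 months", compared between arms. It can be read as a comparison of change from enrolment or of 3-month values.

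Section 20.0 names thrombin peak and thrombin generation as the primary endpoints, without a time point and without saying whether the variable is the 3-month value or the change. Three statements then bear on the analysis:

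- The sample size rests on a two-sample t test at two-sided 0.05 for an "effect size of 0.7 standard deviations in the reduction of thrombin peak or thrombin generation between the two arms".
- "The associations between treatment type and the change in biomarkers will be evaluated using two-sample t test".
- "Linear mixed models will be used to study the associations between the primary endpoints and treatment, and trend across time", with an arm-by-time interaction.

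On covariates there is one sentence: "Potential confounders will be included in the models". No variable is listed.

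The baseline measurement is already planned. The calendar in Section 6.0 marks the row "Thrombin generation assay" at the initial visit, 3 months and 9 months, and the assay is among the research tests in Sections 9.1 and 9.2.

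**The concern.** The 3-month question can be answered in several ways that differ in precision, and nothing fixes the choice before the data are seen.

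The candidates treat baseline differently. A t test on change fixes the slope of the 3-month value on baseline at 1. A t test on the 3-month value fixes it at 0. ANCOVA estimates it. Enrolment samples come from patients with recent VTE, possibly on bridging heparin, and 3-month samples from patients on warfarin or rivaroxaban. Neither a slope of 1 nor equal SDs can be taken for granted.

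The mixed model does not close the gap. If baseline is a response with a free mean in each arm, the 3-month contrast with complete data is the change-score contrast. If both arms share one baseline mean, it is close to ANCOVA. The text does not say which is meant. An overall arm-by-time test also fails to isolate month 3: with categorical time it includes month 9, and with linear time it tests one slope over 0 to 9 months. The sentence on confounders may be meant to cover baseline, but it names no variable and does not apply to a t test.

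**Working it through.** **Inputs from Section 20.0.** 33 evaluable patients per arm, effect 0.7 SD, two-sided alpha 0.05 per endpoint, two-sample t test, 80% power.

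**Assumed inputs, not in the documents.** ρ is the correlation between baseline and 3-month values, shown at 0.3, 0.5 and 0.7. k is baseline SD divided by 3-month SD, shown at 0.5, 1 and 1.5.

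**1. The plan's own figure.** The normal approximation gives 2(1.960 + 0.842)²/0.7² = 32.04, so 33 per arm. The exact calculation has noncentrality 0.7 × √(33/2) = 2.843 on 64 degrees of freedom, and power 79.97%. The stated sample size reproduces.

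**2. Variance of the arm contrast, with the 3-month variance set to 1.**

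- t test on the 3-month value: 1
- t test on change: 1 + k² − 2ρk
- ANCOVA: 1 − ρ²

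In large samples ANCOVA is never worse than either t test. Since (1 + k² − 2ρk) − (1 − ρ²) = (k − ρ)² ≥ 0, it ties with the change score only when ρ = k, that is when the true slope ρ/k equals 1. It ties with the 3-month value only when ρ = 0.

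**3. Cost at this sample size.** ANCOVA has 63 degrees of freedom, and estimating the slope inflates the variance by about 1 + 1/62. Example at k = 1, ρ = 0.5: effect 0.7/√(0.75 × 1.0161) = 0.802, noncentrality 0.802 × √16.5 = 3.257, power 89.4%. All ANCOVA figures below include this cost.

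**4. Reading A: 0.7 is in SDs of the change.** The change t test has 80.0% throughout. The effect in 3-month SDs is 0.7 × √(1 + k² − 2ρk).

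| k | ANCOVA, ρ = 0.3 / 0.5 / 0.7 | t test on 3-month value |
|---|---|---|
| 0.5 | 81.0 / 79.3 / 82.2% | 77.9 / 67.9 / 54.7% |
| 1 | 93.1 / 89.4 / 85.4% | 91.2 / 80.0 / 58.3% |
| 1.5 | 99.4 / 98.9 / 98.6% | 99.0 / 95.9 / 85.2% |

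**5. Reading B: 0.7 is in SDs of the 3-month value.** The 3-month t test has 80.0% throughout. ANCOVA has 82.9 / 89.4 / 97.3% for any k.

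| k | t test on change, ρ = 0.3 / 0.5 / 0.7 |
|---|---|
| 0.5 | 81.9 / 89.9 / 96.5% |
| 1 | 65.8 / 80.0 / 95.1% |
| 1.5 | 44.7 / 56.2 / 74.3% |

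**6. Worst case for ANCOVA.** Where baseline adjustment adds nothing (ρ = 0 under reading B, or ρ = k = 0.5 under reading A), power is 79.3% against 80.0%, a loss of about 0.7 points.

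**7. Simulation check.** With 100,000 trials per setting and the slope estimated, reading A gives 80.7 / 79.5 / 82.3%, 93.2 / 89.3 / 85.4% and 99.4 / 98.9 / 98.7% for the three values of k. Reading B gives 82.7 / 89.4 / 97.3%, and 79.3% at ρ = 0. Type I error at k = 1, ρ = 0.5 is 0.0499.

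**The case against.** **The t test on change is the natural reading.** Section 20.0 speaks of reduction and change, Section 2.0 calls thrombin generation the primary biomarker of interest, and Section 1.1 fixes 3 months. This reading is plausible, and reading B has less support in the text. But the mixed-model sentence is the one that explicitly applies an analysis to the primary endpoints, so the t test cannot simply be presumed primary. Reading A alone also shows the gain at k = 1 and above.

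**A valid, correctly powered t test is acceptable in a pilot.** True. For that reason this is a recommended improvement, not a required correction.

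**ANCOVA is not strictly at least as efficient at 33 per arm.** This stands as a qualification: the statement holds in large samples, and here the loss can reach about 0.7 points. Weak correlation is plausible given the different treatment conditions at enrolment and month 3. Under reading B, ANCOVA then has 79.7% at ρ = 0.1 and 80.9% at ρ = 0.2, so the benefit is negligible.

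**Some of the largest gains come from leaving the change score, not from adjustment.** This also stands. Under reading A at ρ = 0.3, the plain 3-month t test already has 91.2% at k = 1 and 99.0% at k = 1.5, against 93.1 and 99.4% for ANCOVA. But the better t test depends on ρ and k, which are unknown. ANCOVA comes within a point of the better one or beats it in every setting shown.

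**Naming ANCOVA does not remove every choice.** Correct. Section 16.0 has two tube types and at least two reagents, and Section 20.0 leaves log transformation open. The fix has to settle these too.

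**Conclusion.** The point holds, as an efficiency gain and a gap in specification. The planned t test is valid and 33 per arm is right. What is missing is one named 3-month analysis and a stated role for baseline.

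The size of the gain rests on assumed ρ and k. At 33 per arm it runs from a loss of about 0.7 points to gains of 5.4 to 13.1 points over the change t test with equal SDs under reading A (85.4 − 80.0 and 93.1 − 80.0). It is larger if baseline values are more variable than 3-month values. The qualitative conclusion does not depend on those values: ANCOVA risks less than one point, while a poorly matched t test can cost far more, for example 56.2% against 89.4% at k = 1.5, ρ = 0.5 under reading B. The sponsor should make the change.

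**What to change.** In Section 20.0, name one primary analysis for each endpoint: an ANCOVA of the 3-month value on arm and the baseline value of the same parameter, at two-sided 0.05 as already planned. In the same text:

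- Fix in advance the tube type, the reagent and the scale (raw or log), the same for baseline and month 3.
- State a simple rule for missing baseline samples. Alternatively, name as primary the 3-month arm contrast from a mixed model with one baseline mean common to both arms, which keeps those patients. Choose one of the two models, not both.
- Replace the general reference to confounders with a list of any further covariates.
- Keep the arm-by-time analysis as supportive.
- Keep 33 per arm and the 80% power statement.

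The cost is wording, one degree of freedom per model, and under about one point of power if baseline brings nothing. No new data are needed. Section 16.0 holds the plasma for bulk testing at the end of the study, so the model can be fixed before any primary assay result exists.

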## **16.0 Thrombin generation assay**

Blood samples for measurement of thrombin generation will be drawn in vacutainer tubes containing 3.2% sodium citrate with and without corn trypsin inhibitor (CTI) and be processed appropriately within an hour prior to storage. Blood samples will be centrifuged at 2500g (relative centrifugal force) for 15 minutes (min). Plasma will be transferred into plastic tubes, and re-centrifuged at 2500g for 15 min. Plasma will be decanted again after second spin and stored in aliquots of 0.2 mL (platelet poor plasma). The platelet poor plasma will then be snap frozen and stored at -70°C until testing as bulk at the end of the study.

The thrombin generation assays will be performed using a commercial kit (TECHNOTHROMBIN® TGA, Technoclone, Vienna, Austria) according to the manufacturer's instructions in [name] laboratory. The assays are performed based on monitoring the fluorescence generated by thrombin cleavage of a fluorogenic substrate over time, after the activation of the coagulation cascade by tissue factor. At least two reagents will be used. Parameters that will be recorded include: lag phase, time to peak thrombin concentration, peak thrombin concentration, and endogenous thrombin potential (measured by area under the curve).

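### The Bonferroni split of the overall 0.1 alpha is valid, but Holm at the same 0.1 would raise the power to show both primary endpoints at no cost in patients (optional improvement)

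*Combined protocol and SAP*

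**What the plan says.** Section 1.1 of the combined protocol and SAP sets the primary objective as the "reduction of thrombin peak concentration and/or endogenous thrombin potential measured by Thrombin Generation Assay (TGA) at 3 months", comparing the atorvastatin arm with anticoagulation alone. An effect on either parameter therefore meets the objective, and an effect on both is also within it.

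Section 20.0 plans 33 evaluable patients per arm. It claims 80% power for an effect of 0.7 SD "in the reduction of thrombin peak or thrombin generation between the two arms with two-side alpha of 0.05 using a two-sample t test". On multiplicity it says: "An overall alpha of 0.1 for this pilot study was split into 0.05 for each endpoint (thrombin peak and thrombin generation) using Bonferroni method".

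No section names a step-down or other sequential rule, gives a correlation between the two endpoints, or states a power for showing both. Section 20.0 says thrombin generation where Section 1.1 says endogenous thrombin potential (ETP). I read them as the same endpoint. Section 16.0 takes peak concentration and ETP (the area under the curve) from the same assay.

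**The concern.** Bonferroni holds each endpoint at 0.05 even after the other has succeeded. Once one of two hypotheses has been rejected, only one is left to protect, and the full overall alpha can be used for it without breaching the stated 0.1. A plan that stays with Bonferroni gives up this second step.

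What is at stake is limited to the second endpoint. If atorvastatin lowers both peak and ETP, the trial is less likely than it could be to show both with the same patients, samples and overall alpha.

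**Working it through.** **Inputs.** From Section 20.0: two primary endpoints, 33 evaluable per arm, effect 0.7 SD, two-sided 0.05 per endpoint, overall 0.1, two-sample t test. Assumed: bivariate normal data, and a correlation between the endpoints of 0 to 0.95, since the documents give none. As both parameters come from the same assay, the upper part of that range is the more plausible.

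**Step 1: the plan's own figures.**
- Normal approximation: n per arm = 2(1.96 + 0.8416)² / 0.7² = 15.70 / 0.49 = 32.04, rounded up to 33.
- Exact t test: noncentrality 0.7 × √(33/2) = 2.84 on 64 degrees of freedom, power 79.97%.
- Alpha: 0.05 + 0.05 = 0.10.

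All three agree with Section 20.0.

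**Step 2: the two rules.**
- Bonferroni: claim each endpoint with p ≤ 0.05.
- Holm: test the smaller p at 0.1/2 = 0.05. If it is significant, test the larger at 0.1/1 = 0.1. If not, claim nothing.

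Any endpoint with p ≤ 0.05 is claimed under both rules, so Holm never loses a Bonferroni claim. Both rules make at least one claim exactly when the smaller p is ≤ 0.05, so the chance of at least one success is identical.

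**Step 3: Holm keeps the overall error within 0.1 for any correlation.**
- Both effects null: a false claim needs one of the two p values to be ≤ 0.05, with probability at most 0.05 + 0.05 = 0.10.
- One effect null: a false claim needs that endpoint's p to be ≤ 0.1, with probability at most 0.10.

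Simulation gives 9.7 / 9.2 / 7.9% with both null (identical under the two rules) at correlation 0 / 0.5 / 0.8.

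**Step 4: power, 33 per arm, 0.7 SD on both endpoints.** There were 400,000 simulated trials per setting; the Monte Carlo standard error is about √(0.75 × 0.25 / 400,000) = 0.07 points.

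| Assumed correlation | Both, Bonferroni | Both, Holm | Gain (points) | Per endpoint, Bonferroni | Per endpoint, Holm | At least one, either rule |
|---|---|---|---|---|---|---|
| 0.95 | 76.4% | 82.3% | 5.9 | 80% | 82.9% | 83.5% |
| 0.9 | 74.9% | 82.0% | 7.1 | 80% | 83.5% | 85.1% |
| 0.8 | 72.7% | 81.2% | 8.5 | 80% | 84.2% | 87.2% |
| 0.5 | 68.7% | 79.0% | 10.3 | 80% | 85.2% | 91.4% |
| 0 | 64.0% | 76.6% | 12.6 | 80% | 86.3% | 96.0% |

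Internal check: with equal effects, power per endpoint equals (at least one + both) / 2. At 0.8 under Holm this is (87.2 + 81.2) / 2 = 84.2%, as tabulated.

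The gain does not depend on equal effects. With 0.7 and 0.5 SD, power for both goes from 50.4% to 62.3% at correlation 0.8, and from 41.2% to 55.4% at 0.

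**Step 5: the price.** With one real effect (0.7 SD) and one null, the false-claim rate on the null endpoint is 5.0% under Bonferroni and 9.0 / 8.7 / 8.0% under Holm at correlation 0 / 0.5 / 0.8.

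**The case against.** The strongest case for leaving the text alone is that nothing in it is wrong and the plan's own criterion gains nothing. The objective is met by either endpoint, power is stated for one or the other, and on that measure the two rules are identical. Power for both is a target that this review supplies. That stands, and it is why the change is optional. It does not remove the benefit: the objective's wording includes an effect on both, and a pilot that shows both is more informative.

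A second objection is that the whole gain comes from a looser threshold for the second endpoint. That also stands. Such a claim can rest on p between 0.05 and 0.1, where the 95% confidence interval for the arm difference includes zero. Keeping 0.05 for each endpoint is a defensible preference. Against it, the sponsor has already accepted an overall 0.1, and the looser step opens only after the other endpoint has passed 0.05.

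A reader might infer more than the documents support:
- *That the overall error is not controlled, or that the trial is too small.* Neither follows. The split adds to exactly 0.1, and 33 per arm gives the stated 80% per endpoint. No section sets a power target for both.
- *That the assay conditions multiply the primary tests.* Section 16.0 has blood "drawn in vacutainer tubes containing 3.2% sodium citrate with and without corn trypsin inhibitor (CTI" and says "At least two reagents will be used". But no section plans a separate primary test for each tube or reagent, so an error rate for such an analysis would not describe this plan. The same holds for the wording on transformation and mixed models: it leaves detail open but does not breach the 0.1. None of this is part of the point.

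**Conclusion.** The Bonferroni rule is valid, and Holm is a modest improvement at the same overall alpha. At the more plausible correlations of 0.8 to 0.95, power to show both endpoints rises by about 6 to 8.5 points and power per endpoint from 80% to about 83-84%. The larger gains at low correlation (10 points at 0.5, 13 at 0) should carry less weight, since one assay yields both parameters.

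These sizes rest on normal data, 33 evaluable per arm, a true effect of 0.7 SD on both endpoints, and an assumed correlation. The direction of the result and the control at 0.1 hold for any correlation. This is a suggestion for efficiency, not a correction.

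**What to change.** In Section 20.0, replace the Bonferroni sentence by:

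> The overall two-sided alpha of 0.1 is controlled by the Holm method: the smaller of the two p values is tested at 0.05; if it is significant, the larger is tested at 0.1; if not, neither endpoint is significant.

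Keep the sample size sentence. Power at 0.05 is still 80.0% with 33 per arm, and Holm can only add to it.

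The cost is one sentence, with no extra patients or samples and no change to the overall alpha. The sponsor should accept two consequences knowingly: the weaker evidence allowed for a second claim, and the higher false-claim rate on a null endpoint when the other effect is real. If the sponsor prefers 0.05 throughout for those reasons, the present text can stand.

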### 1.2 Secondary Objectives

1.2.1 To determine the composite rate of recurrent VTE and VTE related mortality in patients in the statin arm as compared to no statin arm.

1.2.2 To determine the rate of arterial thrombotic events in patients in the statin arm as compared to no statin arm.

1.2.3 To determine the rate of major, non-major, and all hemorrhages defined by the ISTH (International Society on Thrombosis and Haemostasis) criteria (see section 7.3) in patients in the statin arm as compared to no statin arm.

- 1.2.4 To evaluate the changes in proposed hemostatic, inflammatory, and lipidomic biomarkers at 3 and 9 months compared to upon enrollment in patients in both arms.
- 1.2.5 To determine the rate of residual vein obstruction by Doppler ultrasound at 3 months in patients in the statin arm as compared to no statin arm.
- 1.2.6 To determine the rate of clinical post-thrombotic syndrome (PTS), as objectively evaluated with Villalta scoring system in patients in the statin arm as compared to no statin arm.

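### Clinical events that accrue up to month 9 are compared as crude proportions that ignore follow-up time, with no stated denominator for patients lost early

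*Combined protocol and SAP*

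**What the plan says.** Objectives 1.2.1 to 1.2.3 in section 1.2 ask for event rates by arm. The first reads "To determine the composite rate of recurrent VTE and VTE related mortality in patients in the statin arm as compared to no statin arm"; the other two cover arterial thrombotic events and bleeding. None of the three gives a time point. Section 10.0 makes the month 9 visit the end of the study, and section 6.0 schedules only two visits after enrolment, at months 3 and 9, each with a window of 21 days either way.

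For analysis, section 20.0 says "The secondary endpoints will be compared between the two arms using chi-square test", with Fisher's exact test as the alternative. It also promises frequencies by arm for clinical outcomes and VTE-related events. It names no time-to-event, person-time or competing-risk method. It does not say which patients form the denominator or how someone lost before month 9 is handled.

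On numbers, the same section says "At least 66 evaluable patients will be randomized (1:1 allocation, 33 evaluable patients in each arm", and then "Considering possible drop-outs, our target enrollment will be 80 patients, with 40 on each arm". No drop-out percentage is stated and the word evaluable is not defined.

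Two provisions bear on loss. Section 5.0 lets patients who stop atorvastatin stay in follow-up. Section 8.0 keeps patients with a recurrence in follow-up.

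**The concern.** A chi-square or Fisher test needs one yes/no answer per patient. A patient last seen at month 3 with no event has no answer for months 3 to 9, so the analyst must choose one. Scoring the patient event-free understates the rate. Dropping such patients as non-evaluable discards any event they had before leaving. If evaluable means having the 3-month thrombin sample, a patient who dies of VTE before month 3 would leave the very composite meant to count that death.

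The choice also affects the comparison. The trial is open-label and only one arm takes a study drug, so unequal loss is a credible risk, though not a documented one. If loss differs by arm, or is related to prognosis, the crude contrast can move with no treatment effect behind it. A confidence interval around a crude proportion does not show that error.

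**Working it through.** **The plan's own figures.** The sizing is for the thrombin endpoints: "we anticipate an 80% power to detect an effect size of 0.7 standard deviations in the reduction of thrombin peak or thrombin generation", "with two-side alpha of 0.05 using a two-sample t test".

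- The normal-approximation formula gives 33 per arm. The exact t calculation gives 33.02, with power 0.7997 at 33 per arm. The stated size reproduces.
- Implied allowance: (80 − 66)/80 = 14/80 = 17.5%. This is derived, not stated, and it belongs to endpoints whose objective is at 3 months. It is not a planned 9-month loss for clinical events.

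**Assumptions, because the documents give neither event rates nor drop-out by arm.** The true 9-month risk r is the same in both arms, so there is no treatment effect. The event hazard is constant, h = −ln(1 − r)/9. A fraction d leaves, at times spread evenly over 0 to 9 months and unrelated to prognosis.

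**Step 1: events seen in a drop-out before leaving.** The mean risk up to leaving is m = 1 − r/(9h). For r = 20%, 9h = 0.2231 and m = 1 − 0.2/0.2231 = 0.1037.

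**Step 2: drop-outs kept in the denominator as event-free.** Crude rate = (1 − d)r + d·m.

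- d = 17.5% in both arms: 0.825 × 0.20 + 0.175 × 0.1037 = 18.3%. Both rates are low, but the contrast is not biased.
- d = 25% (statin): 0.75 × 0.20 + 0.25 × 0.1037 = 17.59%.
- d = 10% (control): 0.90 × 0.20 + 0.10 × 0.1037 = 19.04%.
- Difference: 19.04 − 17.59 = 1.4 points, or 0.0144 × 40 = about 0.6 of a patient in an arm of 40.

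The standard error below is √(2r(1 − r)/40).

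| True risk, both arms | Statin, 25% lost | Control, 10% lost | False difference | SE at 40 per arm |
|---|---|---|---|---|
| 20% | 17.6% | 19.0% | 1.4 points | 8.9 points |
| 30% | 26.5% | 28.6% | 2.1 points | 10.2 points |

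**Step 3: timing of loss.** If all losses fall at month 3, a drop-out's risk up to leaving is 1 − 0.8^(1/3) = 0.0717. The rates at r = 20% become 0.15 + 0.25 × 0.0717 = 16.8% and 0.18 + 0.10 × 0.0717 = 18.7%, a difference of 1.9 points. If all fall on day 0, they are 15% and 18%, a difference of 3 points.

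**Step 4: the other denominators, r = 20%, 25% v 10% lost.**

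- Completers only: 20% v 20%. The contrast is unbiased under non-informative loss, but the expected early events discarded are 40 × 0.25 × 0.1037 = 1.0 on statin and 40 × 0.10 × 0.1037 = 0.4 on control.
- Completers plus anyone with a recorded event: 17.59/(75 + 2.59) = 22.7% v 19.04/(90 + 1.04) = 20.9%. Both rates are now high, and the statin arm looks worse.

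**Step 5: wider range.** With drop-out also at a constant hazard and drop-outs scored event-free, risks of 3% to 30% and drop-out (control v statin) from 10% v 25% to 0% v 35% give false differences of 0.2 to 5.3 points, against standard errors of 3.6 to 10 points. Under the extreme 0% v 35% split, the rejection rate of Fisher's test at nominal 0.05 with no true effect is 0.004, 0.019 and 0.052 at risks of 5%, 10% and 30%. With no drop-out it is 0.004, 0.017 and 0.028.

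**The case against.** A reader might infer that the plan counts lost patients as event-free, so that event rates are biased low and the statin arm is flattered. The documents do not support that. Section 20.0 sets no denominator, and step 4 shows that the direction reverses, or the bias in the contrast vanishes, under other choices. Nor is unequal drop-out documented: the arm-specific figures are assumptions, and equal non-informative loss leaves a null comparison at a risk ratio of 1.00.

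The plan also limits loss. Stopping atorvastatin does not end follow-up (section 5.0), nor does a recurrence (section 8.0), and section 12.6 follows patients with adverse events to resolution even after removal from the study. These points stand, but they do not close the gap. Section 5.0 permits continued follow-up without requiring it. Section 8.0 concerns patients whose recurrence has already been counted. Neither reaches an event-free patient who simply stops attending.

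The effect is small. These are secondary endpoints of an 80-patient pilot, and power to detect a halved risk at 40 per arm is roughly 8% (5% v 2.5%), 13% (10% v 5%) and 36% (30% v 15%) by normal approximation. That limits the weight of the point. It is not a reason to keep an avoidable bias.

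Finally, censored methods assume non-informative censoring, so they reduce the problem without removing it. That is correct and shapes the fix.

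**Conclusion.** The point holds in a conditional form. Outcomes that accrue over time are analysed by tests that ignore follow-up time, in a plan that expects drop-outs and does not say how they enter the proportion. The absolute rates can be misstated under either way of forming the proportion. The between-arm contrast is biased only if loss is unequal or informative.

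In the worked example the false difference is 1.4 points at a 20% risk, about 0.16 of a standard error (1.4/8.9). It rests on equal true risks, a constant event hazard, evenly spread loss, assumed drop-out of 25% v 10%, and drop-outs scored event-free. The 9-month horizon is taken from the study's length, since the objectives state none. The 17.5% should not be read as a forecast of 9-month clinical loss.

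The primary thrombin comparison is untouched. This is a cheap improvement to the secondary analysis, not a threat to the trial's main conclusion.

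**What to change.** In section 20.0, for objectives 1.2.1 to 1.2.3:

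- State the horizon (9 months) and include all randomised patients in the arm assigned.
- Analyse time from randomisation to first event, censored at last contact.
- Report 9-month cumulative incidence by arm with 95% confidence intervals: Kaplan-Meier, or Aalen-Johansen with other death as a competing event. Add a log-rank-type test. A permutation version is exact only if censoring is alike in the two arms.
- Report the number, timing and reasons for drop-out by arm, with a simple sensitivity analysis, for example varying the assumed risk after loss by arm. This is needed because the main method assumes non-informative censoring.

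Keep chi-square or Fisher for outcomes read at a fixed visit, such as residual vein obstruction at month 3 and post-thrombotic syndrome, naming the visit for the latter.

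The cost is a few lines of text, plus event and last-contact dates on the data collection forms. No extra patients or visits are needed. The downside is that, with follow-up visits only at months 3 and 9, onset dates of patient-reported minor bleeding may be imprecise.
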